8.2.6. Composite Endpoint

The composite endpoint will be based on a modification to the AD Composite Score (ADCOMS), a composite clinical outcome for prodromal Alzheimer's disease trials [Wang 2016]. Since the assessments collected in this study were not the same as those collected in the published study, the statistician cited on the publication ([name]) assisted in the development of a modified ADCOMS (m-ADCOMS) composite model for this study.

A partial least square regression is performed and validated using data from the Alzheimer's Disease Cooperative Study (ADCS) and from the Alzheimer's Disease Neuroimaging Initiative (ADNI). The proposed model was derived using the original ADCOMS items [Wang 2016] but leaving out the ADAS-COG Word Finding Difficulty and the ADAS-COG Orientation, and substituting the RBANS immediate word recall (LRL) for the ADAS-COG Immediate Word Recall item (after dividing by the total points possible and multiplying by 10) and also the RBANS list recognition (LRN) for the ADAS-COG Recognition item (after dividing by the total points possible and multiplying by 12). The proposed model has an estimated mean square deviation ratio (MSDR) that is more than 95% of the original ADCOMS MSDR.

The same weights as used for the original ADCOMS are used to calculate the composite score for this study:

$$\text{Composite} = \text{LRL} * 0.00847483 + \text{LRN} * 0.003732761 + (5 - \text{M1}) * 0.041567 + (1 - \text{M7}) * 0.038238 + \text{C1} * 0.054321 + \text{C2} * 0.109100 + \text{C3} * 0.089039 + \text{C4} * 0.069493 + \text{C5} * 0.058724 + \text{C6} * 0.078152$$

Scale	Item ID	Item Name
RBANS	LRL	List Recall (LRL)
	LRN	List Recognition
MMSE	M1	Orientation Time
	M7	Drawing
CDR-SB	C1	Personal Care
	C2	Community Affairs
	C3	Home and Hobbies
	C4	Judgment and Problem Solving
	C5	Memory
	C6	Orientation

As the calculation of the composite scores needs to use the CDR-SB scores, which are only collected at baseline and Week 13, the composite scores will be analyzed similarly as for the primary efficacy endpoint at Week 13 only. The composite scores and change from baseline will be summarized by treatment group. The LS Mean and SE of change from baseline in composite scores will also be presented graphically by treatment group.

The pairwise differences in change from baseline between the treatment groups will be assessed and presented, using similar methodology as for the primary efficacy endpoint.

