8.1. Primary Efficacy Endpoint and Analysis – RBANS DMI

The Repeatable Battery for the Assessment of Neurological Status (RBANS) [Randolph 1998] is a brief, individually administered test measuring attention, language, visuospatial/constructional abilities, and immediate and delayed memory. It consists of 12 subtests, which yield five Index scores and a Total Scale score.

Total scores are calculated by adding up the scores for each of the 12 individual subtests and ranges between 0 and 311, where a low score indicates greater impairment. The range of possible scores for the RBANS DMI is 40 to 160.

The primary efficacy outcome measure is the change from baseline to Week 13 in the delayed memory index of the RBANS [Repeatable Battery for the Assessment of Neurological Status - Delayed Memory Index (RBANS DMI)]. Observed cases data (with no imputation for missing values) will be used for primary efficacy analysis.

The original RBANS DMI score and change from baseline will be summarized by treatment group at each time point.

The primary method of analysis will be an MMRM with restricted maximum likelihood estimation, an unstructured covariance matrix, and the Kenward-Roger approximation for denominator degrees of freedom. The model will include fixed effects for treatment, visit (time), the treatment-by-time interaction, ApoE4, pooled study site, the baseline RBANS DMI score as covariate, and a random effect for subject. [Similar models will be defined for the other continuous secondary efficacy endpoints.] Primary inferences will be drawn from treatment differences in the LSmean changes from baseline derived from the MMRM models at Week 13. As additional supportive information, treatment differences for Weeks 1, 4, and 8 will also be derived using the MMRM model. Least Squares Means for each visit and the SE of the LSMeans will be displayed graphically.

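### The SAP does not give the m-ADCOMS composite one consistent derivation: LRL has two names, and the rescaling of LRL and LRN is in the text but not in the formula

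*SAP*

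**What the plan says.** Protocol 11.4 leaves the composite endpoint and its model to be specified in full in the SAP. SAP 4.2 lists the m-ADCOMS among six secondary efficacy outcomes, and SAP 8.2.6 defines it.

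- **Item identity.** The text builds the score by "substituting the RBANS immediate word recall (LRL) for the ADAS-COG Immediate Word Recall item". The item table in the same section gives that item as "List Recall (LRL".
- **Item scale.** The text rescales LRL "after dividing by the total points possible and multiplying by 10" and LRN "after dividing by the total points possible and multiplying by 12". Neither document gives those totals as numbers.
- **Weights.** "The same weights as used for the original ADCOMS are used to calculate the composite score for this study". The formula multiplies LRL by 0.00847483 and LRN by 0.003732761, with no divisor and no factor of 10 or 12. It does write out the MMSE terms as (5 - M1) and (1 - M7).
- **RBANS content.** SAP 8.1 describes an "individually administered test measuring attention, language, visuospatial/constructional abilities, and immediate and delayed memory", with 12 subtests that are not listed.

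**The concern.** A programmer who codes the printed formula and item table literally can produce a score that differs from the one the text describes.

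Immediate and delayed memory are separate RBANS domains, so the two names for LRL could point to different subtests. The original ADCOMS weights also presuppose the original item scale, which is what the factors of 10 and 12 are there to restore. Applied to raw points on another scale, the weights are off by total/10 for LRL and total/12 for LRN.

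SAP 8.3 uses the secondary endpoints as part of the evidence for choosing the Phase 3 dose. An ambiguity still open at unblinding would leave a choice between scores that can have different LS means and p-values.

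**Working it through.** The plan states no maximum or item share for the composite, so there is no figure to reproduce first. I evaluated the formula at the item maxima under both readings.

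**Inputs from SAP 8.2.6 and 8.2.4**

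- CDR weights: 0.054321, 0.109100, 0.089039, 0.069493, 0.058724 and 0.078152, which sum to 0.458829. Each box has a maximum of 3 (six boxes, CDR-SB maximum 18).
- MMSE weights: 0.041567 on (5 - M1), maximum 5; 0.038238 on (1 - M7), maximum 1.
- RBANS weights: 0.00847483 for LRL and 0.003732761 for LRN.

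**Terms that do not depend on the reading**

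- CDR maximum = 3 × 0.458829 = 1.376487
- MMSE maximum = 5 × 0.041567 + 0.038238 = 0.246073
- Sum = 1.622560

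**Rescaled, as in the text**

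- LRL maximum = 10 × 0.00847483 = 0.084748
- LRN maximum = 12 × 0.003732761 = 0.044793
- Together 0.129541, so the composite maximum is 1.752101 and the share is 0.129541 / 1.752101 = 7.4%

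**Raw points, as the formula is printed.** The totals below are assumptions, because the documents give none. The RBANS maximum is LRL total × 0.00847483 + LRN total × 0.003732761.

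| Assumed LRL total | Assumed LRN total | RBANS maximum | Composite maximum | Share |
|---|---|---|---|---|
| 10 | 12 | 0.1295 | 1.7521 | 7.4% |
| 10 | 20 | 0.1594 | 1.7820 | 8.9% |
| 20 | 20 | 0.2442 | 1.8667 | 13.1% |
| 40 | 12 | 0.3838 | 2.0063 | 19.1% |
| 40 | 20 | 0.4136 | 2.0362 | 20.3% |

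Both items keep their intended weight only if the totals are exactly 10 and 12. An LRL total of 10 leaves LRL unaffected by scaling; a total of 40 would overweight it 4-fold.

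**Direction.** SAP 8.1 treats low RBANS scores as worse. SAP 8.2.4 treats high CDR scores as worse, and the formula reverses M1 and M7 to match. LRL and LRN enter with positive weights and no reversal, and the SAP does not say whether they count errors or correct answers. If they count correct answers, perfect recall and recognition would raise (worsen) the composite by 0.1295 on the rescaled reading.

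**Availability of M1 and M7.** The formula needs two MMSE item scores. SAP 8.2.3 says the scores of the individual MMSE tests are not recorded on the CRF. The SAP does not say where M1 and M7 come from.

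**The case against.** The paragraph directly above the formula introduces LRL and LRN together with their rescaling, so the ordinary reading is that the symbols already carry it. The item table gives names only and never says raw points. That is probably what was meant, and on that reading the scale issue comes down to missing totals and a transformation not repeated. It does not remove the point: the same formula prints its MMSE transformations, so leaving out the RBANS ones invites a literal coding error, and the rescaling cannot be carried out from the SAP without the totals.

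Three stronger readings are tempting, and the documents support none of them:

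- **That LRL is two different subtests.** Both entries carry the same identifier, and the subtests are not listed. The documents show only that the item is not uniquely named.
- **That the claim of keeping more than 95% of the original ADCOMS mean square deviation ratio fails.** The SAP says the model was fitted and validated in ADCS and ADNI data. It does not say that those data held RBANS items or that a particular RBANS mapping was tested there, so the documents neither tie the figure to one mapping nor refute it.
- **That the composite is badly distorted.** The 4-fold and 20.3% figures need the less likely raw reading and the largest totals assumed here. Totals of 10 and 12 give no difference.

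The reach is also limited. SAP 8.3 powers the study for the primary endpoint only, and tests a dose's secondary endpoints at nominal p-values only if that dose succeeds on the primary.

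**Conclusion.** The point stands as an inconsistency within SAP 8.2.6, and the full specification promised in Protocol 11.4 is not delivered. LRL has two names that the documents do not equate, and the rescaling is in the text but missing from the formula, with no totals given.

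On the likely intended reading, LRL and LRN together are at most 7.4% of the composite range. On a literal raw reading their share runs from 7.4% to 20.3% over the assumed totals of 10 to 40 for LRL and 12 to 20 for LRN. These are shares of the maximum possible score. They do not estimate any change in a treatment effect or p-value, which the documents do not allow one to compute.

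The scoring direction and the source of M1 and M7 are open in the same derivation. A reader might infer that the formula has the wrong sign for the RBANS items. That follows only if they count correct answers, which the SAP does not state.

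The primary analysis, the sample size and the alpha control are unaffected. The correction should be made, but it concerns one secondary endpoint.

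**What to change.** Revise SAP 8.2.6 before unblinding:

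1. Use one RBANS subtest name for LRL in both the text and the item table, namely the subtest used when the m-ADCOMS model was developed.
2. Print the rescaling in the formula, with the total points possible for LRL and LRN as numbers.
3. State whether LRL and LRN count errors or correct answers. If errors, use 10 × (LRL / LRL total) and 12 × (LRN / LRN total). If correct answers, use 10 × (1 - LRL / LRL total) and 12 × (1 - LRN / LRN total), so that every term runs high = worse.
4. Reconcile the use of M1 and M7 with SAP 8.2.3 by stating where these item scores are recorded.

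Items 1 to 3 cost SAP wording and one derivation line. Item 4 is also only wording if the MMSE item scores are captured somewhere other than the CRF. If they are not, the composite cannot be computed as written, and that needs to be known before unblinding.

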Among the elderly subject cohorts, the percentage of subjects who experienced at least one treatment-emergent adverse event was similar between the 10-mg BID, 20-mg BID, and placebo groups (ranging from 30% to 50%) and was higher for the 40-mg BID dose group (90%). Likewise, the percentage of subjects with at least one drug-related adverse event was also higher for the 40-mg BID dose group (70%) compared with the 10-mg BID dose group (40%), the 20-mg BID dose group (20%), and the placebo group (26.7%). Adverse events reported in 2 or more elderly subjects within a dose group were all reported by subjects in the 40-mg dose group and consisted of diarrhea, increased alanine and aspartate aminotransferase, hot flush (each reported at a frequency rate of 20%) and headache (reported at a frequency rate of 40%). Across the elderly subject cohorts, 2 adverse events (dizziness and hypotension) of moderate severity were reported in 1 of the 10 subjects (10.0%) in the 10 mg BID dose group, and 1 headache of moderate severity was reported in 1 of 10 subjects (10.0%) in the 40-mg BID dose group. Among the elderly subject dose groups, no clinically significant effects of multiple oral doses of BPN14770 (10 mg, 20 mg, or 40 mg) were observed on biochemistry, hematology, or urinalysis; vital signs; or ECGs.

With respect to cognitive testing, BPN14770 10 mg given twice daily was associated with improvement in complex attention/working memory and delayed recall of both visual and verbal information. Treatment with BPN14770 20 mg twice daily was associated with similar benefits as the 10 mg twice daily regimen, excluding improvement in delayed recall of visual information. Neither the 10- or 20-mg BID regimens was associated with improvement in psychomotor function, visual, or verbal learning, or executive function. The 40-mg BID regimen was not associated with improvement in any cognitive domain.

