8.2.3. Mini-Mental State Evaluation (MMSE) Score

The Mini-Mental State Examination (MMSE) is a 30-point questionnaire that is used extensively in clinical and research settings to measure cognitive impairment. It is commonly used to screen for dementia. It consists of a series of questions and tests, each of which scores points if answered correctly. The MMSE tests a number of different mental abilities, including a person's memory, attention and language.

The MMSE [[Folstein 1975](#)] consists of 11 items covering orientation, memory (recent and immediate), concentration, language and praxis. Scores range from 0 to 30, with lower scores indicating greater cognitive impairment. Scores for each of the 11 individual tests are not recorded on the CRF, therefore if any item is missing then the total score will be set to missing.

The maximum MMSE score is 30 points, with lower scores indicating worse disease. A score of 20 to 24 suggests mild dementia, 13 to 20 suggests moderate dementia, and less than 12 indicates severe dementia. On average, the MMSE score of a person with Alzheimer's declines about two to four points each year. (source: https://www.alz.org/alzheimers-dementia/diagnosis/medical_tests)

The MMSE scores will be analyzed similarly as for the primary analysis for the primary efficacy endpoint in [Section 8.1](#), using an MMRM. The MMSE scores and change from baseline will be summarized by treatment group at each time point. The LS Mean and SE of change from baseline in MMSE scores over time will also be presented graphically by treatment group.

The pairwise differences in LS Mean change from baseline between the treatment groups will be assessed at each time point.

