8.2.4. Clinical Dementia Rating Sum of Boxes (CDR-SB) Score

The Washington University Clinical Dementia Rating scale [[Morris 1993](#)] is a structured, clinician-rated interview that collects information on cognitive capacity from both the collateral source and subject for the evaluation of staging severity of dementia. The CDR was developed primarily to assess severity level in persons with dementia but it can be used to stage dementia in other illnesses as well (eg, Parkinson's disease). Six domains are assessed and then synthesized to assign a Global CDR score. The domains are memory, orientation, judgment and problem solving, community affairs, home and hobbies, and personal care. Impairment is defined only when caused by cognitive loss rather than by physical disability or other non-cognitive factors. Severity ratings range along a 5-point scale (except for the personal care domain):

This document is confidential.

- CDR-0: no cognitive impairment
- CDR-0.5: questionable or very mild dementia
- CDR-1: mild
- CDR-2: moderate
- CDR-3: severe

The CDR is frequently utilized in clinical and research settings to describe stage-dependent features of dementia and for use as a clinically-meaningful outcome measure in clinical drug trials.

CDR is an ordinal parameter (scale 0-3) and is only collected at baseline and Week 13. The CDR sum of boxes (CDR-SB) score is obtained by summing each of the domain box scores, with scores ranging from 0 (least impairment) to 18 (severe impairment).

The CDR-SB score (and each individual domain) will be analyzed similarly as for the primary analysis for the primary efficacy endpoint in [Section 8.1](#). The CDR-SB score and change from baseline will be summarized by treatment group. The LS Mean and SE of change from baseline in CDR-SB scores will also be presented graphically by treatment group.

The pairwise differences in change from baseline between the treatment groups will be assessed at Week 13.

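### The printed m-ADCOMS formula leaves its two RBANS items unreversed in a higher-is-worse score, so better list recall or recognition counts as worsening

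*SAP*

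**What the plan says.** Protocol section 11.4 leaves the full definition of the composite to the SAP, so SAP section 8.2.6 is the governing specification. Its formula reads "LRL} * 0.00847483 + \text{LRN} * 0.003732761 + (5 - \text{M1}) * 0.041567 + (1 - \text{M7}) * 0.038238", followed by the six CDR boxes C1 to C6, each with a positive weight and no reversal.

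The directions of the component scales are given elsewhere in the SAP:

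- **CDR (8.2.4):** the sum of boxes is described "with scores ranging from 0 (least impairment) to 18 (severe impairment", so higher is worse.
- **MMSE (8.2.3):** scored "with lower scores indicating greater cognitive impairment", so higher is better.
- **RBANS (8.1):** "Total scores are calculated by adding up the scores for each of the 12 individual subtests", on a scale "where a low score indicates greater impairment", so higher is better.

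The derivation of the RBANS recall item is described as "substituting the RBANS immediate word recall (LRL) for the ADAS-COG Immediate Word Recall item (after dividing by the total points possible and multiplying by 10"; the recognition item is treated the same way, with 12 in place of 10. No other transformation is given for either item.

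SAP section 4.2 lists the composite among six secondary endpoints. Section 8.3 treats the secondary endpoints as part of the evidence for dose selection, and tests them for a dose only if that dose succeeds on the primary endpoint.

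**The concern.** The formula aligns direction item by item. CDR boxes enter as they stand, and the two MMSE items are subtracted from their maxima, so the total is a higher-is-worse score. LRL and LRN carry positive weights like the CDR boxes, but they come from a scale where higher is better and have not been subtracted from their maxima. Any gain on the two list items is therefore set against the benefit shown by CDR and MMSE, and a memory benefit is diluted or partly cancelled in an endpoint used for dose selection.

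Three inputs are also not pinned down:

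- The text of section 8.2.6 calls LRL immediate word recall, while its item table calls it list recall.
- The rescaling needs the maximum score of each RBANS item, and neither is given.
- The formula needs MMSE items M1 and M7, but section 8.2.3 says "Scores for each of the 11 individual tests are not recorded on the CRF".

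**Working it through.** The SAP gives no numerical result for the composite, so there is no figure to reproduce. The check evaluates the formula at its extremes and for some worked changes, once as printed and once with the RBANS items reversed.

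**Inputs (SAP 8.2.6).** Weights: LRL 0.00847483, LRN 0.003732761, M1 0.041567, M7 0.038238. CDR boxes: 0.054321 + 0.109100 + 0.089039 + 0.069493 + 0.058724 + 0.078152 = 0.458829. Ranges: LRL 0 to 10 and LRN 0 to 12 after rescaling; M1 0 to 5; M7 0 to 1; each CDR box taken as 0 to 3.

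**Maximum contribution of each part**

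- RBANS: 10 × 0.00847483 + 12 × 0.003732761 = 0.0847 + 0.0448 = 0.1295
- MMSE: 5 × 0.041567 + 0.038238 = 0.2461
- CDR: 3 × 0.458829 = 1.3765
- Aligned total: 0.1295 + 0.2461 + 1.3765 = 1.7521

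**Extremes**

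| Subject | As printed | With (10 - LRL), (12 - LRN) |
|---|---|---|
| Perfect on every item | 0.1295 | 0 |
| Perfect on MMSE and CDR, zero on both RBANS items | 0 | 0.1295 |
| Worst on every item | 0.2461 + 1.3765 = 1.6226 | 1.7521 |

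As printed, the subject who recalls and recognises nothing scores better than the subject with no deficit at all.

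**Changes from baseline.** The constants 10 and 12 cancel in a change score, so only the sign matters. A gain of fraction f of maximum on both RBANS items moves the composite by +f × 0.1295 as printed and by -f × 0.1295 when aligned.

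- f = 0.10 (assumed): +0.013 instead of -0.013.
- f = 7.15/120 = 0.0596 (assumed, the planned DMI difference over the 40 to 160 range): +0.0077 instead of -0.0077.
- Two rescaled points on each item: 2 × (0.00847483 + 0.003732761) = 0.0244, so +0.0244 instead of -0.0244.
- The same two-point gains with a half-point improvement in CDR Memory (0.5 × 0.058724 = 0.0294): -0.0294 + 0.0244 = -0.0049 (from unrounded values) as printed, against -0.0538 aligned.
- Gain on both RBANS items that fully cancels that half point: 0.0294 / 0.1295 = 22.7% of maximum.

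**Share and dilution.** The RBANS share of the aligned range is 0.1295 / 1.7521 = 7.4%. If every item improved by the same fraction of its range (assumption), the printed change would fall short by twice that share, 14.8%. If CDR boxes are also assumed to stay at or below 1, the range is 0.1295 + 0.2461 + 0.4588 = 0.8344, the share 15.5% and the shortfall 31.0%.

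No standard deviation is given for the composite, so the effect on power cannot be computed.

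**The case against.** The strongest reply is that the direction of LRL and LRN is inferred. The statement in section 8.1 is about the RBANS total, and no section gives the direction of either item or of the composite. Section 8.2.6 puts the RBANS items in the place of two ADAS-COG items and keeps the original weights. That would also fit a derivation in which they are coded in the direction of the items they replace, so the program may already count items missed. This stands as a limit: the documents show that the printed formula is misaligned, not that the endpoint will be computed wrongly. It does not rescue the text. A total formed by adding subtests, with low meaning impaired, implies that each list subtest is better when higher. A score divided by the points possible reads as points earned. Nothing in the plan defines either item as errors.

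The size is also open to challenge. Only the 7.4% share and the per-point shifts follow from the formula alone. Equal proportional improvement is an assumption. Inclusion restricts the CDR score to 0.5 or 1 but does not cap individual boxes, so the 15.5% and 31.0% figures are illustrative. The 6% case carries a fraction of an age-normed index range over to a subtest, which the documents do not support.

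The consequence is limited too. CDR-SB and its domains, MMSE, RBANS total and the RBANS indices are each analysed separately, so the composite would not hide a benefit seen there. The expected drug effect on the list items is unclear. Protocol section 4.3.2.2 reports "Neither the 10- or 20-mg BID regimens was associated with improvement in psychomotor function, visual, or verbal learning, or executive function", yet the same section reports better delayed verbal recall at both doses, and the subtest meant by LRL is not identified.

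Finally, the M1 and M7 question is one of data availability. Scores not on the CRF may be held elsewhere. It is a separate gap and adds nothing to the sign error.

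**Conclusion.** The concern holds for the formula as printed. In a score where higher is worse, the two RBANS items enter in the opposite direction, so a subject who improves on them is scored as worse. The error is confined to two of ten items and does not reverse the composite. It offsets a true benefit, by 14.8% under equal proportional improvement and by an unknown amount otherwise. The conclusion rests on one inference, that LRL and LRN are points earned, which the SAP's wording supports and nothing in it contradicts. The primary RBANS DMI analysis is unaffected, and the composite is tested only for a dose that succeeds on the primary. It should be fixed because the SAP is the only full definition of this endpoint, and following it literally gives wrong scores.

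**What to change.** Before unblinding, amend SAP section 8.2.6 to state that a higher composite is worse and to define how LRL and LRN are coded.

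- If they are points earned, replace them with (10 - LRL) and (12 - LRN) after rescaling.
- If the derivation program already uses items missed, define them that way and do not reverse again.

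In either case, name the RBANS subtest meant by LRL, give the maximum score of both items, and confirm that the stated MSDR of more than 95% of the original was obtained with the aligned scoring. State where the M1 and M7 item scores are held.

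The cost is SAP wording and at most one line of derivation code. The reversal needs no new data, but the availability of M1 and M7 must be checked first, because the composite cannot be calculated without them. Made before unblinding, this is a routine correction; made afterwards, it could look like a data-driven change to the endpoint.
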